1. OBJECTIVES

1.1. Primary Objective

The primary objective of the study is to determine if near-infrared fluorescence imaging of panitumumab-IRDye800 can identify metastatic disease in regional neck lymph nodes of subjects with head and neck squamous cell carcinoma (HNSCC).

1.2. Secondary Objective

Determine if panitumumab-IRDye800 can identify sentinel nodes with the same accuracy as Lymphoseek.

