STATISTICAL CONSIDERATIONS	
To answer the primary objective we will calculate the sensitivity and specificity of the intraoperative findings on whether the lymph node is fluorescent (ie, presence of panitumumab-IRDye800) to the histopathological (gold standard) status of the lymph nodes.
 
Analysis for the secondary objective: We will determine if panitumumab-IRDye800 can identify sentinel nodes with the same accuracy as Lymphoseek. Similar to the primary analysis, we will calculate the specificity and sensitivity of Lymphoseek for metastatic lymph node identification, using histology as the gold standard, and compare these to the fluorescence imaging-based results. Since false negatives are of particular concern, we will calculate the diagnostic odds ratio to better understand the odds of obtaining a false negative using panitumumab-IRDye800 relative to the odds of obtaining a false negative using Lymphoseek-based sentinel node biopsy.

STUDY SCHEME

[figure not shown]

Figure 1. Schematic overview of the clinical trial in which we will directly compare panitumumab-IRDye800 to the reference standards sentinel node biopsy and neck dissection. Key steps of the clinical study are mentioned.

LIST OF ABBREVIATIONS AND DEFINITION OF TERMS

^{99m} Tc	Technetium-99m
AE	Adverse Event
BID	Twice Daily
BSA	Body Surface Area
CBC	Complete Blood Count
CI	Confidence Interval
CMAX	Maximum Concentration of Drug
CNS	Central Nervous System
CRF	Case Report/Record Form
CT	Computed Tomography
CTCAE	Common Terminology Criteria for Adverse Events
DLT	Dose-Limiting Toxicity
DSMC	Data Safety Monitoring Committee
ECG	Electrocardiogram
ECOG	The Eastern Cooperative Oncology Group
EGFR	Epidermal Growth Factor Receptor
eLND	Extensive Lymph Node Dissection
FDA	Food and Drug Administration
GMP	Good Manufacturing Practice
Hgb	Hemoglobin
HNSCC	Head and Neck Squamous Cell Carcinoma
HTN	Hypertension
ICG	Indocyanine green
ILD	Interstitial Lung Disease
IND	Investigational New Drug
IRB	Institutional Review Board
IV	Intravenous
LLN	Lower Limit of Normal
LN	Lymph Node
MTD	Maximum Tolerated Dose
NIR	Near-Infrared
NHS	N-hydroxysuccinimide
PAI	Photoacoustic imaging
PLT	Platelet
ROI	Region of Interest
SAE	Serious Adverse Event
SN	Sentinel Node
SNB	Sentinel Node Biopsy
SNR	Signal to Noise Ratio
SPECT	Single Photon Emission Computed Tomography
TBR	Tumor to Background Ratio
ULN	Upper Limit of Normal
UNK	Unknown
WBC	White Blood Cell
WHO	World Health Organization

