2. BACKGROUND

2.1 Study Disease

Squamous cell carcinoma of the head and neck affects more than 61,760 people in the United States annually, with a 5-year survival rate being <60% (1,2). **The presence of lymph node (LN) metastasis is considered the most important negative prognostic factor for survival in patients with primary HNSCC (3,4).** Despite advanced anatomic and metabolic imaging techniques, occult LN (micro-) metastasis remain in the clinically and radiographically negative neck (cN0). In fact, 10 to 30% of cN0 patients present with occult LN metastasis (4). Even more so, treatment of the neck is often indicated when the risk of LN metastasis exceeds 15 to 20% (5,6). To address this surgically, the current NCCN guidelines recommend either elective regional neck node dissection or sentinel node (SN) biopsy (SNB) (7).

Elective lymph node dissection causes significant morbidity: The gold standard for detection of regional metastatic disease in HNSCC traditionally has been a (elective) neck dissection. However, shoulder dysfunction and pain due to accessory nerve (cranial nerve XI) injury are common after neck dissection (8–11). Moreover, 60 to 80% of subjects undergoing a neck dissection with sectioning of the nerve have pain, limited abduction of the shoulder, and anatomic deformities such as scapular flaring, droop, and protraction (12). To reduce morbidity, there has been a gradual migration away from extensive dissection to more limited dissection offered by SNB where only the primary tumor draining LN(s) are removed for detailed histologic examination (13–18). SNB has already replaced regional lymphadenectomy in melanoma and breast surgery to avoid the associated deficits associated with this more aggressive approach, and is now also advocated for HNSCC (7).

Sentinel node biopsy: SNB is performed as a surgical staging method to detect occult nodal disease in those tumor types with a high metastatic rate and where LN disease predicts outcome and informs adjuvant treatment decisions. Assuming the orderly spread of tumor cells through the lymphatic system (19), excision and evaluation of the primary tumor-draining LNs only (so-called SN(s)) will allow accurate determination of the tumor status of the regional LNs in the neck. SNB thus allows the selection of node-positive subjects that will benefit from additional surgical or adjuvant therapy, while sparing node-negative patients an unnecessary neck dissection.

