Sentinel node biopsy vs elective regional node dissection: Besides decreased morbidity, SNB offers other advantages over a neck dissection: i) Identification of aberrant draining patterns and “skip metastasis” (35–37); and ii) Improved (micro-) metastasis identification at (histo-)pathology; fewer SNs are harvested which are more meticulously evaluated by the pathologist, resulting in improved diagnostic accuracy (38,39). However, challenges remain: i) Local tracer injection is complicated in areas deep in the oral cavity; ii) Near-injection site SN identification can be challenging due to overshadowing of signal at the primary tumor signal (40,36,22); iii) Often multiple SNs are identified during surgery (22) increasing the risk of complications (41) (eg, nerve damage, lymphedema, scar tissue formation); iv) neck dissection after a positive SNB is complicated due to the presence of scar tissue; and v) A false-negative SNB occurs in 3 to 10% of subjects (ie, the SN is tumor-negative, but at follow-up metastasis in remaining regional LNs are found (42–45). Moreover, although LN mapping is superior to radiographic and clinical exam, it is still limited by the need for direct injection of the dye or radiolabeled compound. **Upstaging with LN assessment can thus only be assessed in tumor types that are accessible for local injection.** This is significant because it influences standard of care (LN surgery or complete lymphadenectomy) in these subject populations only. Identification of regional disease will inform prognostic information and/or determine the need and extent of adjuvant therapies for additional tumor types. Most importantly, however, the tracers used for SNB are not tumor-specific and thus SNB, similar to neck dissection, does not allow for intraoperative tumor-positive LN identification (21,46,47). In fact, **for both SNB and neck dissection (histo-)pathological evaluation is required to determine the presence of (micro-) metastasis and thus a method to intraoperatively identify metastatic LNs is lacking.** Thus, HNSCC subjects would benefit from an alternative technique that, allows for intraoperative lymph node staging.

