3. Hereafter, as per standard of care, the surgeon will perform SNB using the gamma probe. For this, the surgeon will evaluate the neck with the gamma probe for the presence of radioactive nodes. Upon localizing of radioactive nodes, the count rate of the node will be determined. Then, just prior to the resection of the radioactive node, *in situ* fluorescence imaging will be performed to evaluate the fluorescence-based visibility of the node. For each radioactive node, the respective *in situ* location will be documented (level Ia, Ib, IIa, IIb, III, IV or V) as well as the radioactive status (count rate) and fluorescence status (yes/no). Hereafter the node will be harvested by the surgeon. This process will be repeated until no radioactive nodes are detected anymore *in situ*.

Step 2) Wound bed imaging:

As per standard of care SNB, upon completion of SNB, the neck will be screened once more with the gamma probe as such to determine the presence of any remaining radioactivity (ie, a radioactive signal detected > 10% of the background that correlates with any substrate (node). Areas in the wound bed determined radioactive-positive will be surgically re-evaluated, and, upon checking the fluorescence-status, removed, if deemed necessary by the surgeon. If any nodes are found, gamma tracing will be performed to determine the radioactive status.

Step 3) Pathological imaging:

The fluorescence and/or radioactive status of all excised nodes will be confirmed *ex vivo* on the back table using both a closed-field imaging device and an open-field device as well as the gamma probe, respectively. Hereafter all excised nodal specimens will be sent for (histo-)pathology. After the tissue has been processed and evaluated by the pathologist, imaging findings will be compared to gold-standard histological-assessment performed by the pathologist (including a hematoxylin and eosin (H&E) staining) to determine the correlation between fluorescence, radioactivity and the presence/absence of tumor tissue in the LN(s). Also findings will be compared to preoperative lymphoscintigraphy and SPECT/CT imaging (ie, correlation between preoperative imaging findings and intraoperative imaging findings).

Neck dissection only (T1-4, cN+)

After the neck has been opened by the surgeon, it will be inspected by the surgeon for the presence of suspicious nodes. Real-time fluorescence imaging of the LNs in the neck will then be performed at 4 time points:

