10.2 Secondary Outcome Measure

The **secondary objective** of the study is to determine if panitumumab-IRDye800 can identify LNs with the same accuracy as Lymphoseek.

The **secondary endpoint** is: The number and location of Lymphoseek positive LNs that are also tumor-positive at (histo-)pathology. Comparison of the number and location of Lymphoseek positive LNs that are also tumor-positive at (histo-)pathology vs the number and location of panitumumab-IRDye800 positive LNs that are also tumor-positive at (histo-)pathology.

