12.1.2. Secondary Objective and Endpoint

The **secondary objective** of the study is to determine if panitumumab-IRDye800 can identify LNs with the same efficiency as Lymphoseek.

The **secondary endpoint** is: The number and location of Lymphoseek positive LNs that are also tumor-positive at (histo-)pathology.

To answer the secondary objective: We will determine if the LN tracer Lymphoseek can identify metastatic disease in regional neck LNs of subjects with HNSCC. Similar to the primary analysis, we will calculate the specificity and sensitivity of Lymphoseek for metastatic LN identification, using histology as the gold standard, and compare these to neck dissection with Durkalski's test. Since false negatives are of particular concern, we will calculate the odds of obtaining a false negative using panitumumab-IRDye800 relative to the odds of obtaining a false negative using Lymphoseek-based SNB.

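### The secondary objective is about sentinel nodes, but both tracers are scored only against tumor histology, and the Lymphoseek comparison can expect only about 1 to 3 node-positive subjects

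*Combined protocol and SAP*

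**What the plan says.** **Objective.** Section 1.2 and the synopsis state it as "Determine if panitumumab-IRDye800 can identify sentinel nodes with the same accuracy as Lymphoseek". Section 10.2 restates it as "to determine if panitumumab-IRDye800 can identify LNs with the same accuracy as Lymphoseek", and section 12.1.2 as "to determine if panitumumab-IRDye800 can identify LNs with the same efficiency as Lymphoseek".

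**Endpoint.** Section 12.1.2 gives "The number and location of Lymphoseek positive LNs that are also tumor-positive at (histo-)pathology". Section 10.2 adds a comparison with the corresponding panitumumab-IRDye800 nodes.

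**Analysis.** The synopsis says "we will calculate the specificity and sensitivity of Lymphoseek for metastatic lymph node identification, using histology as the gold standard", and compares the results with fluorescence. Section 12.1.2 plans the same sensitivity and specificity, but its Durkalski test compares Lymphoseek with neck dissection. Both places add a comparison of the odds of a false negative with each tracer. Section 12.1.1 applies a 0.05 significance level to secondary analyses. No margin is given for sameness.

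**Who and what is measured.** Table 1 and section 4.1 give Lymphoseek to Cohort 1 only: 10 subjects, T1 or T2, cN0. Section 3.1 calls this the SNB-only cohort. Under section 2.4.3.3 the surgeon marks fluorescent nodes on a photograph of the opened neck, then removes radioactive nodes until none can be detected. Neck level, count rate and fluorescence (yes or no) are recorded for each radioactive node.

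**Background.** Section 2.1 describes sentinel nodes as the nodes that drain the primary tumor and says that "the tracers used for SNB are not tumor-specific". It also states that "10 to 30% of cN0 patients present with occult LN metastasis".

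**The concern.** A sentinel node is defined by drainage, and most sentinel nodes in a cN0 neck contain no tumor. Histology answers a different question: whether a node is metastatic. With histology as the only reference, the dye gains specificity for each tumor-free sentinel node it fails to show and loses specificity for each one it shows. Section 2.4.3.5 expects some non-specific uptake by a mechanism like sentinel-node mapping, so such nodes are likely to occur.

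Two features of Cohort 1 add to this. Nodes enter the data because they are radioactive, which largely fixes Lymphoseek's scores in advance. And few of these subjects will have a tumor-positive node. The trial could then report sensitivity, specificity and a p-value under the heading of the secondary objective without having measured how often the dye finds a sentinel node, and with almost no information on whether the tracers differ in sensitivity.

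**Working it through.** **1. The plan's own power figures (section 12.1.3).** Inputs: 600 nodes, 20 subjects, intra-class correlation 0.005, prevalence 7.5%, discordance 0.25.

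- Nodes per subject: 600/20 = 30. Effective sample size: 600/[1 + (30 − 1) × 0.005] = 600/1.145 = 524. This reproduces.
- Effective tumor-positive nodes: 524 × 0.075 = 39.3. Exact one-sided McNemar power for a 0.2 difference in sensitivity (discordant cells 0.225 and 0.025) is 76.8% at 39 nodes and 78.1% at 40, in line with the stated 78%.
- Tumor-negative nodes: 524 × 0.925 = 485. Power for a 0.1 difference in specificity, by normal approximation, is 99.8% one-sided and 99.4% two-sided. This reproduces.

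These figures use nodes from all 20 subjects. Ten of those subjects never receive Lymphoseek, so the figures do not describe the Lymphoseek comparison.

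**2. Subjects who inform sensitivity in the Lymphoseek comparison.** Expected number = 10p. P(none) = (1 − p)^10. P(at most one) = (1 − p)^10 + 10p(1 − p)^9.

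| Rate p | Source | Expected | P(none) | P(at most one) |
|---|---|---|---|---|
| 10% | 2.1, lower end | 1 | 0.349 | 0.736 |
| 20% | 2.1, midpoint | 2 | 0.107 | 0.376 |
| 30% | 2.1, upper end | 3 | 0.028 | 0.149 |
| 34% | 2.1, upstaging in the cited multicenter SNB series | 3.4 | 0.016 | 0.097 |
| 40% | 12.1.3, upper end, both cohorts pooled | 4 | 0.006 | 0.046 |

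**3. What so few can show.** Assume one tumor-positive node per such subject. If all k positive nodes are discordant in the same direction, the one-sided exact p-value is 0.5^k: 0.125 for k = 3 and 0.0625 for k = 4. Significance at 0.05 is out of reach with four or fewer. A perfect 3 of 3 has an exact 95% lower limit of 0.025^(1/3) = 29%. If subjects contributed several positive nodes and the total reached 10, the plan's own discordance and difference would give exact one-sided power of 4.5%, before any allowance for clustering.

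**4. How the scoring treats sentinel nodes.** Assumed for illustration: 20 radioactive nodes, 2 of them tumor-positive.

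| Agent | Sentinel nodes found | Sensitivity vs histology | Specificity vs histology |
|---|---|---|---|
| Lymphoseek | 20/20 = 100% | 2/2 = 100% | 0/18 = 0% |
| Dye lighting only the 2 metastatic nodes | 2/20 = 10% | 2/2 = 100% | 18/18 = 100% |
| Dye lighting all 20 | 20/20 = 100% | 2/2 = 100% | 0/18 = 0% |

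The second dye misses 90% of sentinel nodes and has a perfect score.

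**5. Lymphoseek's scores are set by sampling.** Section 2.4.3.3 removes nodes in Cohort 1 because they are radioactive. A tumor-positive node without radioactivity normally stays in the neck and has no histology, so Lymphoseek's false negatives are largely unobservable. A fluorescent, non-radioactive node is marked on the photograph, but no step provides for its removal, so a metastasis seen by the dye and missed by Lymphoseek would usually not be confirmed either. The comparison of false-negative odds is therefore barely estimable.

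**The case against.** The strongest reply is that metastatic nodes were always the target. The title says so. Section 2.4.1 gives the comparison with Lymphoseek for metastatic-node identification as the reason for enrolling cN0 subjects. Sections 10.2 and 12.1.2 speak of lymph nodes, not sentinel nodes, and section 2.1 reports Lymphoseek's false-negative rate against tumor. Tumor specificity is also listed as the dye's advantage over SNB. This stands as evidence that metastatic-node detection may also be intended, so the histology comparison should stay. It does not remove the mismatch, because the synopsis and section 1.2 name sentinel nodes.

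A reader might infer that the plan would hide any disagreement between the tracers. That goes too far. The objective is comparative: a dye that lit exactly the radioactive nodes would match Lymphoseek on both measures, and a dye that missed tumor-free sentinel nodes would differ in specificity. The disagreement would register, but as better specificity rather than as missed sentinel nodes. Step 3 of the sentinel node procedure in section 2.4.3.3 also plans to correlate fluorescence, radioactivity and tumor, though not as an endpoint and with no stated measure.

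A reader might also infer that only 1 to 3 subjects inform sensitivity in the whole trial, or that tumor-negative subjects contribute nothing. The documents support neither. Primary fluorescence sensitivity also uses the ten cN+ subjects, and tumor-negative nodes inform specificity.

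Finally, section 12.1.3 counts 20 nodes in each of 30 necks across both cohorts, as if Cohort 1 were dissected too. If so, Lymphoseek's false negatives could be observed. Sections 3.1 and 2.4.3.3 provide only for SNB in that cohort, and the number of node-positive subjects would remain small either way.

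**Conclusion.** The concern holds as a mismatch between the sentinel-node objective and a histology-only endpoint, made worse by the way Cohort 1 nodes are sampled. In the Lymphoseek comparison, 1 to 3 subjects are expected to inform sensitivity, or up to about 4 at the documents' higher rates. The chance of none is 35%, 11% and 3% at occult rates of 10%, 20% and 30%. A finding of no significant difference there could not support a claim of equal accuracy.

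The counts assume 10 evaluable Cohort 1 subjects and independence between them. The significance limit in step 3 assumes one positive node per subject, and the 20-node table is illustrative. The documents do not support the stronger conclusion that histology is the wrong reference and should be replaced: section 2.4.1 gives it a legitimate purpose. What is missing is a measure that matches the sentinel-node wording.

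**What to change.** - **Synopsis, 10.2 and 12.1.2:** add, as the measure for the sentinel-node objective, the proportion of radioactive (Lymphoseek-defined) nodes in Cohort 1 that are fluorescent. Report it per node with a subject-clustered 95% confidence interval, and per subject (all radioactive nodes fluorescent; at least one fluorescent). Beside it, report the number and neck level of fluorescent nodes that were not radioactive.
- **Histology comparison:** keep the two tracers' detection of metastasis as a separate, stated objective. In Cohort 1, report estimates with confidence intervals and make no claim of equal accuracy.
- **12.1.2:** remove or correct the Durkalski comparison of Lymphoseek with neck dissection, since under the plan the SNB-only cohort has no neck dissection.
- **Wording:** state the objective identically in the synopsis, 1.2, 10.2 and 12.1.2.

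Cost: text changes only. Fluorescence and radioactivity are already recorded for each node under section 2.4.3.3, so no new procedure or subject is needed. The downside is one more secondary measure, and a Lymphoseek metastasis comparison limited to estimation. The new measure will also be imprecise. Assuming 2 to 3 sentinel nodes per subject (section 2.1 says only that there are often several), 20 to 30 nodes would contribute. For example, 18 of 25 fluorescent is 72%, with an exact 95% interval of 51% to 88% before allowing for clustering. That describes agreement; it does not establish sameness.

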2. BACKGROUND

2.1 Study Disease

Squamous cell carcinoma of the head and neck affects more than 61,760 people in the United States annually, with a 5-year survival rate being <60% (1,2). **The presence of lymph node (LN) metastasis is considered the most important negative prognostic factor for survival in patients with primary HNSCC (3,4).** Despite advanced anatomic and metabolic imaging techniques, occult LN (micro-) metastasis remain in the clinically and radiographically negative neck (cN0). In fact, 10 to 30% of cN0 patients present with occult LN metastasis (4). Even more so, treatment of the neck is often indicated when the risk of LN metastasis exceeds 15 to 20% (5,6). To address this surgically, the current NCCN guidelines recommend either elective regional neck node dissection or sentinel node (SN) biopsy (SNB) (7).

Elective lymph node dissection causes significant morbidity: The gold standard for detection of regional metastatic disease in HNSCC traditionally has been a (elective) neck dissection. However, shoulder dysfunction and pain due to accessory nerve (cranial nerve XI) injury are common after neck dissection (8–11). Moreover, 60 to 80% of subjects undergoing a neck dissection with sectioning of the nerve have pain, limited abduction of the shoulder, and anatomic deformities such as scapular flaring, droop, and protraction (12). To reduce morbidity, there has been a gradual migration away from extensive dissection to more limited dissection offered by SNB where only the primary tumor draining LN(s) are removed for detailed histologic examination (13–18). SNB has already replaced regional lymphadenectomy in melanoma and breast surgery to avoid the associated deficits associated with this more aggressive approach, and is now also advocated for HNSCC (7).

Sentinel node biopsy: SNB is performed as a surgical staging method to detect occult nodal disease in those tumor types with a high metastatic rate and where LN disease predicts outcome and informs adjuvant treatment decisions. Assuming the orderly spread of tumor cells through the lymphatic system (19), excision and evaluation of the primary tumor-draining LNs only (so-called SN(s)) will allow accurate determination of the tumor status of the regional LNs in the neck. SNB thus allows the selection of node-positive subjects that will benefit from additional surgical or adjuvant therapy, while sparing node-negative patients an unnecessary neck dissection.

Typically, to identify the SN(s) preoperatively, a local injection of a non-tumor specific radiotracer is given around the primary tumor followed by lymphoscintigraphy to visualize

drainage of the radiotracer through the lymphatic system to the SN(s) (20–22). The addition of single photon emission computed tomography combined with computed tomography (SPECT/CT) was shown to allow for localization of the SN within its anatomical context, providing the surgeon with a 3D map to plan the surgical procedure (22). During the surgical procedure, these SN(s) can then be identified and excised using a gamma ray detection probe that localizes the radioactive signal in the nodes (20,23). More recently, mobile gamma cameras were introduced to provide the surgeon with additional (visual) feedback with regard to having localized and removed the radioactive LNs (24).

Meta-analysis of SNB in breast cancer, head and neck cancer, and melanoma have validated the accuracy of SNB in predicting occult LN metastasis (13,17,25,26). More recently, for HNSCC, the validity of the approach was also shown. In a large multicenter study including 227 SNB procedures from 6 centers, Alkureishi *et al.*, showed that the procedure was successful in 93% subjects whereby in 34% (42 subjects) of cases HNSCC subjects were upstaged whereby in 10 subjects only micro-metastasis were present (27). Where the centers participating in the Alkureishi *et al.*, paper used colloid-based SN tracers, more recently a mannose-receptor targeting tracer for SNB was introduced, Lymphoseek (28–34). In head and neck cancer, using Lymphoseek an even higher sensitivity was reported: in 98% of subjects (81/83) at least one SN could be found with false-negative rate of 2.6% (ie, tumor-positive LN was not detected by Lymphoseek) and a negative predictive value of 98% (28).

Sentinel node biopsy vs elective regional node dissection: Besides decreased morbidity, SNB offers other advantages over a neck dissection: i) Identification of aberrant draining patterns and “skip metastasis” (35–37); and ii) Improved (micro-) metastasis identification at (histo-)pathology; fewer SNs are harvested which are more meticulously evaluated by the pathologist, resulting in improved diagnostic accuracy (38,39). However, challenges remain: i) Local tracer injection is complicated in areas deep in the oral cavity; ii) Near-injection site SN identification can be challenging due to overshadowing of signal at the primary tumor signal (40,36,22); iii) Often multiple SNs are identified during surgery (22) increasing the risk of complications (41) (eg, nerve damage, lymphedema, scar tissue formation); iv) neck dissection after a positive SNB is complicated due to the presence of scar tissue; and v) A false-negative SNB occurs in 3 to 10% of subjects (ie, the SN is tumor-negative, but at follow-up metastasis in remaining regional LNs are found (42–45). Moreover, although LN mapping is superior to radiographic and clinical exam, it is still limited by the need for direct injection of the dye or radiolabeled compound. **Upstaging with LN assessment can thus only be assessed in tumor types that are accessible for local injection.** This is significant because it influences standard of care (LN surgery or complete lymphadenectomy) in these subject populations only. Identification of regional disease will inform prognostic information and/or determine the need and extent of adjuvant therapies for additional tumor types. Most importantly, however, the tracers used for SNB are not tumor-specific and thus SNB, similar to neck dissection, does not allow for intraoperative tumor-positive LN identification (21,46,47). In fact, **for both SNB and neck dissection (histo-)pathological evaluation is required to determine the presence of (micro-) metastasis and thus a method to intraoperatively identify metastatic LNs is lacking.** Thus, HNSCC subjects would benefit from an alternative technique that, allows for intraoperative lymph node staging.

We propose to evaluate the fluorescently-labelled anti-EGFR antibody, panitumumab-IRDye800, for its ability to intraoperatively identify sentinel and LN (micro-)metastasis. We propose to directly compare fluorescence imaging of panitumumab-IRDye800 imaging findings to that of SNB and neck dissection whereby we will use (histo-)pathology as gold standard for determining the true tumor-positive LNs.

Potential benefits of panitumumab-IRDye800 for metastatic LN identification over SNB:

- 1) Panitumumab-IRDye800 is a tumor-targeted tracer that can allow intraoperative identification of metastatic lymph nodes (for the other techniques pathology is required to confirm).
- 2) Panitumumab-IRDye800 is systemically injected, and thus can allow metastatic LN identification also at sites that are not-accessible for a SN tracer (ie, tumor in the hypopharynx).
- 3) Panitumumab-IRDye800 provides a tumor-specific approach whereas the SN tracer is not tumor-specific.
- 4) Panitumumab-IRDye800 can be injected several days before the operation and thus scheduling logistics would be improved (SN tracer is preferable injected the day of surgery)
- 5) If successful with the optical dye, similar studies could be conducted with a radiolabeled dye.

Fluorescent, tumor-targeted antibodies for intraoperative cancer detection: Clinical data has provided evidence that novel tumor-targeted antibodies can improve detection, and survival in a variety of cancer types (48). By fluorescently labelling these antibodies (eg, using the near-infrared fluorescent dye IRDye800) it was shown that the sensitivity and specificity of (microscopic) tumor detection in the operative setting could be significantly improved (49–52). Improved visualization can thus significantly improve surgical techniques and outcome.

The epidermal growth factor receptor (EGFR) is found overexpressed in 80 to 90% of subjects with HNSCC (53). Our group has shown that EGFR-based optical imaging can detect subclinical disease (non-palpable tumor) within the resection bed approximately 72 hours after systemic administration of a fluorescently labeled anti-EGFR antibody (54–56). The potential of optical imaging to guide surgical resection by capitalizing on the overexpression of EGFR has also been supported by the findings of other groups in a variety of solid tumors (57–59). Moreover we've shown the feasibility of real-time fluorescence imaging-based identification of HNSCC using the anti-EGFR antibody cetuximab-IRDye800 (49,60,61). In our phase 1 study, in all subjects, tumor tissue could be clearly discriminated from normal tissue, and a high fluorescence intensity strongly correlated with the presence of tumor (36,41). **Moreover, we showed that with another anti-EGFR antibody, cetuximab-IRDye800 we could identify metastatic LNs with a high 97.2% sensitivity; 92.7% specificity; 99.7% negative and 50.7% positive predictive value (62).** More recently we switched to panitumumab-IRDye800 – our phase 1 study (IRB-35064) evaluating the safety and dosing of panitumumab-IRDye800 in HNSCC is reaching completion. Preliminary results of this phase 1 study are in line with our previous clinical studies using cetuximab-IRDye800 and suggests that we will be able to

identify LNs via near-infrared fluorescence imaging of panitumumab-IRDye800 not detectable by conventional white light (Figure 2).

[figure not shown]

Figure 2: Near-infrared fluorescence imaging-based lymph node identification in a subject with HNSCC. Upper three panels: Brightfield (left); fluorescence (middle); and overlay (right) image showing a cluster of LNs in the neck. Lower panels: Evaluation of a formalin-fixed tumor-positive and tumor-negative LN illustrating differences in panitumumab-IRDye800 uptake.

Although EGFR is clearly a good target for HNSCC, we chose to abandon cetuximab-IRDye800 and move forward with another near-infrared fluorescence labeled antibody, panitumumab-IRDye800, because: 1) Panitumumab is a fully humanized anti-EGFR-antibody resulting in fewer infusion reactions (cetuximab Grade 1-2 infusion reactions are as high as 30% (63,64); 2) Panitumumab is a member of the IgG2 subclass of IgG proteins in human serum, which have lower complement activation and low Fc receptor binding, and thus induces minimal inflammation and toxicity; 3) Tumor-to-background ratios obtained with panitumumab-IRDye800 are similar, if not better, than with cetuximab-IRDye800 (65); and 4) Panitumumab displays an improved safety profile; we have only seen one Grade 1 adverse event reported in 37 subjects that were infused with panitumumab-IRDye800 (IRB-35064) compared to 15 Grade 1 adverse events in 12 subjects that were given cetuximab-IRDye800 (NCT01987375). In addition, in the phase 1 cetuximab-IRDye800 study, in 2 subjects the study drug was not given because of an infusion reaction to cetuximab (66,67).

